**Justification for exclusion criteria:**

1. Genitourinary abnormalities, diseases or surgical procedures may have an impact on the results of data and catheterization may be unnecessary uncomfortable for the subjects.
2. To ensure that the subjects do not have UTI at inclusion. In the event of UTI, catheterisation would be unnecessarily uncomfortable. None of the symptoms may be present.
3. To eliminate uncertainty whether any Adverse Events (AE's) or Serious Adverse Events (SAE's) occurring during the study relate to the use of the herein tested products, and to eliminate unintentional effect from other devices/medicines on this study's data.
4. Unnecessary harm for the subjects.
5. To eliminate the risk of UTI in pregnant or breastfeeding women.

**6.3.3. Recruitment and enrolment**

Recruitment of potential subjects will begin once approval have been obtained from the Ethics Committee of the Capital Region Denmark and the Danish Medicines Agency.

Investigator identifies potential subjects in relation to in- and exclusion criteria, through subject records kept at the site (from previous clinical studies involving healthy subjects, who have expressed interest in future clinical investigations). The identified potential subjects will receive written subject information and "Forsøgspersoners rettigheder i et sundhedsvidenskabeligt forskningsprojekt". If the subject is interested in participating, an information meeting is arranged.

Subjects may furthermore be recruited through [www.forsogsperson.dk](http://www.forsogsperson.dk) where potential subjects can gather information on clinical studies. If necessary, they may also be recruited through local newspapers and social medias. Interested potential subjects must contact the Clinical Manager at Coloplast A/S or a representative hereof. In- and exclusion criteria are reviewed and general questions regarding the study are answered. If the potential subject is interested in participating, he/she will receive the written subject information and "Forsøgspersoners rettigheder i et sundhedsvidenskabeligt forskningsprojekt" and contact information is passed on to investigator or study nurse, who will contact the potential subject. If he/she still wishes to participate, an information meeting is arranged.

The informed consent process is described in Section 13.

#### **6.3.4. Subject withdrawal criteria**

The subject can withdraw from the clinical investigation at any time for whatever reason without any consequences for their future treatment outside the investigation. The investigator may withdraw a subject from the investigation at any time if the investigator judge withdrawal to be in the subject's interest.

The investigator must withdraw a subject from the evaluation for the following reasons:

- Non-compliance with the Clinical Investigation Plan impacting the scientific integrity of the evaluation.
- If a subject's safety and well-being is compromised by further participation.

A subject who is withdrawn from the investigation, for any reason, will be encouraged to contact the investigator if problems arise that the subject believes are related to the investigation

#### **6.3.5. Point of enrolment**

A subject is considered enrolled in the investigation when the written informed consent is obtained.

#### **6.3.6. Total expected duration of the clinical investigation**

The dates below are approximate, and no subjects will be enrolled before all required approvals have been obtained.

- Submission to EC and CA: October 2018
- Amended submission: March 2019
- First patient in: March 2019
- Last patient out: August 2019
- Report: August 2020

#### **6.3.7. Total number of subjects**

12 healthy volunteers will be enrolled in this study. Both male and female are eligible for enrolment. No differences between male and female data are expected, but since the final device should comply with both male and female catheters, it is decided to include both male and female in the study.

Minimum 4 subjects of each gender must be enrolled. The reason for this to eliminate an outlying data curve relation to gender.

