### Population

The population consists of 12 healthy volunteers. Both male and female are eligible for enrolment. Minimum 4 subjects of each gender must be enrolled and subjects must comply with the following inclusion and exclusion criteria:

Inclusion criteria:	Exclusion criteria:

 
1. Have given written informed consent
 
2. Be at least 18 years of age and have full legal capacity
 
3. Negative pregnancy test for fertile women
 
	
 
1. Previous history of significant genitourinary disease including congenital abnormalities and surgical procedures performed in the urinary tract
 
2. Symptoms of urinary tract infections (frequent urination, stinging and pain at urination)
 
3. Participation in any other clinical investigations during this investigation (Inclusion → termination)
 
4. Known hypersensitivity toward any of the test products
 
5. Are pregnant (positive pregnancy test) or breast feeding.
 

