### **6.1.4. Discussion of clinical investigation design**

This is a single arm, open-labelled, not randomized investigation. The population consists of 12 healthy volunteers. Both male and female are eligible for enrolment. Minimum 4 subjects of each gender must be enrolled for one test visit. The reason for this design is the exploratory nature of the investigation.

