## **Visit 1 – Test – approximately one hour**

Subjects are requested to meet for this visit with a fairly full bladder (avoided urination within 2 hours prior to the visit) or they will be offered a large glass of water and wait for this to reach the bladder. Fertile females will be asked to perform a pregnancy test. Subjects are asked about symptoms for urinary tract infections (frequent urination, stinging or pain at urination). If negative for these symptoms, the subject will be catheterised with SpeediCath® Standard, male/female, Nelaton tip depending of the gender after the sensor has been connected onto the catheter. The bladder will be emptied via a catheter into a standard urine flowmeter, measuring urine flow, by a nurse.

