#### **Analysis of primary endpoint**

Sensor data will be graphically presented over time and sensor capability to generate a readable sensor profile will be visually evaluated (FAS) and considered versus what is known on bladder physiology.

In case of an unexpected profile, the sensor profile will be considered in relation to the data on urine flow and voided volume, obtained via a standard uroflow meter.

Readable sensor profiles versus non-readable sensor profiles will be summarized.

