## **7.3. Drop-out**

As this study only consist of one study visit, expected drop-outs are 0. Should there be a drop-out, will these be replaced until 12 patients has finalised visit 1.

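### Does the plan need a by-gender readability summary, and a gender minimum counted on tested rather than consented subjects?

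*Combined protocol and SAP*

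**What the plan says.** The minimum of four per gender appears three times. Section 6.3.7 gives it with its reason: "Minimum 4 subjects of each gender must be enrolled. The reason for this to eliminate an outlying data curve relation to gender". The synopsis (Population) has "Minimum 4 subjects of each gender must be enrolled and subjects must comply with the following inclusion and exclusion criteria", and section 6.1.4 has "Minimum 4 subjects of each gender must be enrolled for one test visit". Section 6.3.5 fixes the meaning of the counted unit: "A subject is considered enrolled in the investigation when the written informed consent is obtained".

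Section 7.3 expects no drop-outs and adds: "Should there be a drop-out, will these be replaced until 12 patients has finalised visit 1". It sets no condition on the gender of a replacement.

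On why both genders take part, section 6.3.7 expects no difference between male and female data, but "since the final device should comply with both male and female catheters, it is decided to include both male and female in the study". Under Visit 1 in section 6.4.1 the catheter is "male/female, Nelaton tip depending of the gender after the sensor has been connected onto the catheter", so gender and catheter type coincide in every subject.

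For the primary endpoint, section 7.1 plans a graphical presentation over time, a visual evaluation, and one tabulation: "Readable sensor profiles versus non-readable sensor profiles will be summarized". No split by gender or catheter is mentioned.

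**The concern.** There are two separate worries.

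**Counting unit.** The reason for the minimum is about data curves, but the unit counted is consented subjects. Consent comes at Visit 0. The pregnancy test and the check for urinary symptoms come at Visit 1, before catheterisation, and a subject may withdraw at any time (section 6.3.4). A subject can therefore be enrolled and never produce a curve. If four women consent, one is lost and a man replaces her, the enrolment minimum and the 12 completed visits are both met with only three female curves.

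**Summary.** Both genders are recruited because the device must work with both catheters, yet the only tabulation named has no row for each. A pooled 8/12 could mean the sensor worked throughout with one catheter and never with the other, or that failures were scattered. With no pass/fail criterion, the study's value lies in guiding sensor development, and these two patterns would send that work in different directions.

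**Working it through.** The plan has no calculation to reproduce: section 7.2 says no formal sample size calculation was done, and no readability rate or power is stated. The inputs from the documents are 12 completers, at least 4 per gender and an expected drop-out of 0. Loss rates, the gender mix of replacements and all readability counts below are assumptions for illustration.

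**1. What a pooled count can conceal.** The most uneven permitted split is 8:4. If 8 of 12 profiles are readable, with k readable in the group of 4 and 8 − k in the group of 8, then k can be 0, 1, 2, 3 or 4. That gives five patterns, from 0/4 with 8/8 to 4/4 with 4/8, all pooling to 8/12 = 66.7%.

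**2. What a by-gender row could show.** If f non-readable profiles fell at random among the 12, the chance that all lie in the group of 4 is C(4,f)/C(12,f):

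| f | Calculation | Chance |
|---|---|---|
| 1 | 4/12 | 33.3% |
| 2 | 6/66 | 9.1% |
| 3 | 4/220 | 1.8% |
| 4 | 1/495 | 0.2% |

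Three or four failures confined to the smaller group would stand out; one or two would not be interpretable. Exact 95% intervals are 0% to 60% for 0/4 and 40% to 100% for 4/4, so the row would be descriptive only.

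**3. Whether such a pattern could stay hidden.** Section 6.5.1 has pressure and flow plotted for each catheterisation and the data quality judged by eye. Section 7.1 repeats the visual evaluation for the full analysis set. Gender is recorded (flow-chart, section 6.4.4) and baseline data are summarised and listed (section 7.1). The report must critically evaluate all data collected (section 16). The gross failure that step 2 could detect is four flat or unusable curves out of 12, all from one gender. Anyone reading 12 plots against the listing would see it.

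**4. Chance of fewer than four tested in one gender.** Let s be the starting size of the smaller gender and p the chance of loss after consent. Each of the 12 places ends with one completer. If replacements are equally likely to be of either gender, a place keeps its original gender with probability 1 − p + p/2 = 1 − p/2. The final number in the smaller starting gender is Bin(s, 1 − p/2) + Bin(12 − s, p/2). The chance that either gender ends below 4 is:

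| Starting split | p = 0 | p = 2% | p = 5% | p = 10% |
|---|---|---|---|---|
| 8:4 | 0 | 3.6% | 7.9% | 12.7% |
| 7:5 | 0 | 0.1% | 0.5% | 1.6% |
| 6:6 | 0 | <0.01% | 0.05% | 0.3% |

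If the site replaces like with like, every entry is 0.

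**The case for a change.** The strongest case for a change is that the plan makes gender, and with it catheter type, a deliberate design factor and then does not commit to reporting by it. A split that a reader can rebuild from listings is not one that must be reported, and choosing it after seeing the curves is weaker than naming it beforehand. The cost would be a few sentences and two table rows from data already collected. On counting, the defined term does say consent, and one route to loss, the pregnancy test, affects only women.

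Much of this is true as description. No by-gender row is prespecified, and the defined term is used loosely. But a pooled-only analysis is inferred from silence: section 7.1 says profiles will be summarised and does not exclude a breakdown. Prespecification guards against selective inference, and there is no test, threshold or success criterion here (sections 7.2 and 7.4) for it to protect. On counting, section 6.1.4 ties the minimum to the test visit and section 6.3.7 ties it to data curves, so the intended unit is clear. The gap needs a gender at its minimum, or brought down to it, a loss from that gender and a replacement from the other. Visits 0 and 1 may also fall on the same day, which shortens the time for loss.

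The obvious rewording could also do harm. If the minimum counted only subjects with a completed sensor recording, a subject who was catheterised but whose sensor recorded nothing would drop out of the count and could be replaced. That is arguably the plainest failure of the primary endpoint, so the rule would favour working sensors. That subject has also finished Visit 1, so a replacement would be a thirteenth, while section 11 supplies 12 devices, one per subject.

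**Conclusion.** No change follows. The missing by-gender row is a gap that analysts would fill sensibly. With 12 individually plotted profiles and gender listed, a failure large enough for the row to reveal would already be visible, and smaller imbalances would not be interpretable with groups as small as four. Followed as written, the plan still supports its exploratory conclusion. Giving readable n/N by gender in the report, labelled descriptive, would be sensible and needs no amendment.

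The wording of the minimum is a clerical looseness that section 6.1.4 largely resolves. Its exposure is zero at the plan's expected drop-out. It reaches 12.7% only from an 8:4 split with an assumed 10% loss and replacement without regard to gender, and is at most 1.6% from 7:5 or 6:6. These figures assume independent losses at the same rate in both genders. The documents give no loss rate other than the expected zero.

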### **6.4. Procedures**

#### **6.4.1. Clinical investigation-related procedures**

Before initiation of the clinical investigation, sponsor must be provided with key personnel's signed and dated curriculum vitae (not more than two years old) to verify their qualifications. Key site personnel are those, who treat or evaluate subject data in the clinical investigation. Also, the sponsor will ensure that all site personnel are trained in the investigation procedures, how to complete the CRFs, procedure for reporting an adverse event or serious adverse event, and who to contact in case of emergency related to the investigational device.

The investigation consists of an inclusion visit and one test visits. For an overview see flow-chart in section 6.4.4.

## **Visit 0 - Inclusion - approx. 30 min**

### Information:

If a potential subject is interested in participating, an information visit will be arranged in a room reserved to ensure privacy and quiet surroundings at the site.

When arranging the visit, it will be ensured, that the subject has received the Subject Information Form prior to the visit and the subjects will receive both written and verbal information about the possibility of bringing a companion to the informational visit and to any possible subsequent visits. During the information visit, the Investigator or delegated personnel, will provide oral information about the investigation based on the Subject Information Form. The subjects have the right to wait 24h before deciding on participation. The information visit and the Visit 0 can be the same day.

### Informed consent:

If/when the subject decides to participate he will be asked to sign the Informed Consent Signature Form and other relevant forms (see section 13). If a subject so desires, and it is certain that it is understood what the investigation entails and the relevant forms have been signed, it is then ensured that in- and exclusion criteria are met. Enrolled subjects are allocated a subject number, baseline data and concomitant medications is recorded by Investigator or delegated personnel.

Visit 0 and Test Visit 1 can be combined.

## **Visit 1 – Test – approximately one hour**

Subjects are requested to meet for this visit with a fairly full bladder (avoided urination within 2 hours prior to the visit) or they will be offered a large glass of water and wait for this to reach the bladder. Fertile females will be asked to perform a pregnancy test. Subjects are asked about symptoms for urinary tract infections (frequent urination, stinging or pain at urination). If negative for these symptoms, the subject will be catheterised with SpeediCath® Standard, male/female, Nelaton tip depending of the gender after the sensor has been connected onto the catheter. The bladder will be emptied via a catheter into a standard urine flowmeter, measuring urine flow, by a nurse.

### **Termination – end of visit 1**

Subjects who leave the study will continue to "Termination", at which the PI or a person delegated by the PI will complete the Termination form. The study is completed by completion of visit 1 and the Termination form will be completed by the end of visit 1 at the latest. Except from the Medical care of subjects described in section 14.5, no follow up or data capture will be conducted after the subject has left the study.

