### 5.2. Risks and anticipated adverse device effects to be assessed

Risks associated with the investigation may be discomfort or stinging in the urethra during the catheterisation. Furthermore, there may be a risk of micro-trauma and haematuria after catheterisation, which is expected to heal within 1-3 days. The trial setting is not expected to result in increased frequency or severity of the known risks associated with urethral catheterisation

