**Exclusion criteria:**

1. Previous history of significant genitourinary disease including congenital abnormalities and surgical procedures performed in the urinary tract
2. Symptoms of urinary tract infections (frequent urination, stinging and pain at urination)
3. Participation in any other clinical investigations during this investigation (Inclusion → termination)
4. Known hypersensitivity toward any of the test products
5. Are pregnant (positive pregnancy test) or breast feeding.

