#### 6.4.4. Flow-chart

	PERFORMED BY	SOURCE	INFORMATION AND INCLUSION VISIT 0	VISIT 1	TERMINATION END OF VISIT 1
General					
Oral information	Investigator	NA	X		
Signed informed consent	Subject	Informed consent form	X		
Signed Letter of authority	Subject	Letter of Authority Form	X		
Signed secrecy agreement	Subject	Secrecy form	X		
Concomitant medication registered	Investigator	CRF	X		
Check of in- and exclusion criteria	Investigator	CRF	X		
Allocation to subject number and sensor serial number	Investigator	CRF	X		
Insurance of subjects well-being and compliance with CIP	Investigator	CRF	X	X	X
Registration of Baseline data					
Date of birth	Investigator	CRF		X	
Gender	Investigator	CRF		X	
Check for symptoms of UTI before catheterisation					
Check for symptoms of UTI (frequent urination, stinging and pain at urination)	Investigator	CRF		X	
Catheterisation	Investigator	CRF		X	
Registration of measurements					
Sensor data prior to and during voiding.	Investigator	Data points		X	
Urine flow profile (uroflowmeter) - Max flow rate (mL/s) - Middle flow rate (mL/s) - Voiding time (s) - Flow time (s) - Time to max flow (s) - Voided volume (mL)	Investigator	Printed graph		X	
AEs/ADEs/SAEs/SADEs	Investigator	CRF		X	X
Registration of termination					
Termination form. Completed	Investigator	CRF			X

Table 1 chart showing the connection between visits and assessments

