### **14.5. Medical care of subjects**

Principal investigator shall ensure that adequate medical care is provided to a subject experiencing an adverse event during and after participation in the clinical investigation. All serious adverse events will be followed until a resolution is addressed.

Subjects are informed to contact investigator if any adverse event should occur during the investigation. Furthermore, investigator will inform the subjects to contact him should serious adverse events occur within one week of the subject is terminated from the study. Subjects are informed to contact their general physician in case of any adverse event(s) happening later than one week of investigation termination.

The status of all ongoing adverse events is documented during site close-out.

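### Non-serious adverse events that begin or are first noticed after the one-hour test visit are not solicited, although adverse events are the only secondary endpoint

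*Combined protocol and SAP*

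**What the plan says.** - **Endpoint.** Section 6.1.2 names AEs as the only secondary endpoint. Section 7.1 plans a summary and a listing on the safety set. Neither gives a time window.
- **Schedule.** In Table 1 (section 6.4.4) the row "AEs/ADEs/SAEs/SADEs" is marked under Visit 1 and under Termination, a column defined as the end of Visit 1. There is no mark at Visit 0 and no later column. Section 6.4.1 gives the length of Visit 1 as "approximately one hour".
- **After the visit.** The termination text in section 6.4.1 ends the study for a subject at completion of Visit 1, and after that: "Except from the Medical care of subjects described in section 14.5, no follow up or data capture will be conducted".
- **Contact instructions.** Section 14.5 first states: "Subjects are informed to contact investigator if any adverse event should occur during the investigation". For the next period, "investigator will inform the subjects to contact him should serious adverse events occur within one week of the subject is terminated from the study". AEs arising more than a week after termination are directed to the general physician. The same section has the status of ongoing AEs documented at close-out.
- **Anticipated effects.** Section 5.2, headed "Risks and anticipated adverse device effects to be assessed", says that "there may be a risk of micro-trauma and haematuria after catheterisation, which is expected to heal within 1-3 days". Table 2 (section 14.2) lists macroscopic haematuria (band 2-10%) and UTI (band 0-1%) as anticipated adverse device effects.
- **Reporting.** Section 14.6.1 has the principal investigator assess all AEs at the site, and has adverse device effects reported to the sponsor within 10 days on a form.

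**The concern.** The request to subjects narrows from any AE to serious AEs at the moment they go home. Effects of a catheterisation may first appear or be noticed after that point. A non-serious haematuria or UTI noticed at home reaches the AE listing only if the subject calls without having been asked to.

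At stake is the completeness of the only secondary endpoint, and how its result is read. An AE listing without a time label could be taken to cover the effects the plan says it will assess, when the scheduled recording covers only events up to the end of Visit 1.

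**Working it through.** The plan states no figure on this point that could be reproduced, and section 7.2 says that no formal sample size calculation was done. The check sets the instructions side by side and then sizes the gap from the plan's own risk bands.

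**Step 1. What is asked for, by period**

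| Period | Scheduled recording (Table 1) | Subject's contact instruction (14.5) |
|---|---|---|
| Visit 1 to its end | Yes | Any AE, to the investigator |
| First week after termination | None | Serious AEs only, to the investigator |
| Later than one week | None | Any AE, to the general physician |

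A non-serious AE first noticed in the middle period falls under no instruction. The first instruction in 14.5 could cover that week only if the investigation were still running for the subject. Section 6.4.1 ends it at Visit 1, and exclusion criterion 3 uses the same span: "during this investigation (Inclusion → termination". A separate serious-only rule for the week would also be hard to explain if the general rule already applied.

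**Step 2. Which events fall in the gap**

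- Haematuria seen at Visit 1 is recorded, and its status is documented at close-out. It is not lost, even if it heals days later.
- Haematuria that begins or is noticed after the visit, and UTI following the catheterisation, are not solicited. If the site hears of them, 14.6.1 applies.
- Stinging or pain during catheterisation (Table 2) falls inside the scheduled recording.

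**Step 3. How many events could be involved**

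Inputs: n = 12 (section 6.3.7) and the Table 2 bands, which are risk ratings and not observed rates. The share s of events with post-visit onset or notice is not given, so it is assumed over its full range.

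Expected post-visit cases = 12 × p × s. Chance of at least one = 1 − (1 − p × s)^12.

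| Haematuria, assumed s | p = 2%: expected; chance | p = 10%: expected; chance |
|---|---|---|
| 0 | 0; 0% | 0; 0% |
| 0.25 | 0.06; 1 − 0.995^12 = 5.8% | 0.30; 1 − 0.975^12 = 26.2% |
| 0.50 | 0.12; 1 − 0.99^12 = 11.4% | 0.60; 1 − 0.95^12 = 46.0% |
| 1 | 0.24; 1 − 0.98^12 = 21.5% | 1.20; 1 − 0.90^12 = 71.8% |

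UTI at the top of its band with s = 1: 12 × 0.01 = 0.12 expected cases, and 1 − 0.99^12 = 11.4%.

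**Step 4. What an empty listing would show**

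With complete ascertainment, 0 of 12 gives a one-sided 95% upper bound of 1 − 0.05^(1/12) = 22.1%. If only a fraction r of events is reported, the bound on the true rate is 22.1%/r. For assumed r = 0.75 it is 29.5%, and for r = 0.5 it is 44.2%. At r = 0 there is no bound. The listing is descriptive even at best, and for post-visit events it weakens as reporting falls.

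**The case against.** A short window can be defended. The sensor does not touch the subject and the catheter is already on the market (section 2.1.4). Section 5.2 closes by saying that the trial setting should not make the known risks of catheterisation more frequent or more severe. Section 6.4.1 states the visit-only rule openly. The study is exploratory, has no pass/fail criterion (section 7.4), and only lists and summarises AEs. This stands as a reason to keep the importance low. It does not supply the missing time label, and Table 2 still counts haematuria and UTI as anticipated device effects.

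The 1-3 days in section 5.2 are time to heal, not time to onset. This stands in full: only late-onset or late-noticed cases are at issue, and no document gives their share. The range in the working therefore starts at zero, and its top needs both the upper edge of the band and every case arising after the visit.

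Other provisions reach past the visit: the close-out check of ongoing AEs, the investigator's duty to assess all AEs, and the 10-day rule for adverse device effects. These stand too, and they confine the gap. They act on events the site already knows of, and none of them tells anyone to ask.

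Finally, the subject information was not in the text available, and section 13 is partly redacted. The wording given to subjects may be broader than section 14.5. This limits confidence.

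**Conclusion.** The point holds as a gap in solicitation. Non-serious AEs that begin or are first noticed in the week after Visit 1 are not asked for, so the secondary endpoint may miss those that subjects do not volunteer. On the Table 2 bands this is 0 to 1.2 expected haematuria cases and at most 0.12 UTI cases in 12 subjects. The true size is unknown because the post-visit share and the rate of volunteered reports are unknown. The primary endpoint is unaffected and no formal decision rests on AEs.

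A reader might infer more than the documents support:

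- That post-visit AEs cannot be recorded. Section 14.6.1 gives known adverse device effects a route and a form, and its duty to assess all AEs has no stated time limit.
- That haematuria is missed because it takes days to heal. A case seen at the visit is counted.
- That serious AEs or medical care lapse after the visit. Section 14.5 provides for both.

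Importance is minor to moderate. Confidence is moderate, because the consent wording could not be checked and the reading of section 14.5 rests on the end of study given in section 6.4.1.

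**What to change.** Reconcile the termination text in 6.4.1, Table 1, 14.5 and 14.6.1:

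1. In 14.5, extend the existing one-week contact from serious AEs to any AE, recorded on the AE form. This is a data-collection instruction and alters nothing about care. One week is proposed only because the plan already uses it.
2. State that window for the secondary endpoint in 6.1.2, 7.1 and Table 1. Reconcile its start as well: the safety population in 7.1 begins at informed consent, while Table 1 has no AE mark at Visit 0.
3. In the report, describe post-visit AEs as subject-initiated and possibly under-reported, so that an empty listing is not read as proof that none occurred.

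If the sponsor prefers the visit-only window, label the endpoint as AEs up to the end of Visit 1 and draw no conclusion on post-visit haematuria or UTI.

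Cost: a short amendment, notified to or approved by the ethics committee and the authority, since section 9 counts changes to endpoints or assessment methods as significant. The subject information changes if it repeats 14.5. A few more AE forms are needed for 12 subjects, and no extra visit. Database lock moves by about one week, against the 12 months in section 6.3.6 between last patient out (August 2019) and the report (August 2020).
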